1.4 Dose Rationale and Risk/Benefits

The dose of the megestrol was based upon the preliminary clinical data published.

CONFIDENTIAL

This material is strictly confidential and is intended solely for the guidance of clinical investigation. Do not disclose or use except as authorized in writing by the study sponsor

2 Study Aims

The primary aim of the current study is to conduct a randomized controlled trial of a 4-week course of megestrol, the only remaining medication that is part of the iKanEat protocol, to ensure that the addition of megestrol results in improved child outcomes. The second aim is to assess the safety of megestrol as part of the iKanEat protocol. Our previous work (as well as work by others) suggests that a 6 week course of megestrol can lead to adrenal insufficiency in some children (11-14), so as part of the current protocol, we will assess the safety of a 4 week course of this drug.

Finally, parents of tube fed children encounter multiple psychosocial stressors regarding tube feeding (15). These include concerns about their child's survival due to their underlying medical issues, feelings of "failure" due to their inability to feed their child orally (16), increased feelings of stress around the tube feeding (17) and decreased support from others due to the tube feeding (18,19). Our research indicates that quality of life can be poor in tube fed children (11), even more so than children with cancer or burns. Given the significance of these issues, the third aim of the study is to examine the effect of the transition from tube to oral feeding on parent stress and parent and child quality of life.

Aim 1: To assess the efficacy of megestrol as part of the 24 week iKanEat protocol.

Hypothesis 1: Children randomized to the megestrol group will be significantly more successful in making the transition to oral feeding (defined as obtaining at least 90% of calories orally) than children randomized to the placebo group.

Aim 2: To assess the safety of 4 weeks of megestrol as part of the 24 week iKanEat protocol.

Hypothesis 2A: Children randomized to the megestrol group will not differ from control children in morning cortisol classification level (low, average, high) and will remain within the normal range at all time points.

Analyses 2B: Exploratory analysis will determine which, if any, covariates (gender, age, and diagnoses at week 0, diagnoses at birth) are related to abnormal morning cortisol levels.

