3.4 Primary Safety Endpoints

Safety Interviews

To monitor for negative side effects, patients will be interviewed during clinic visits and tele-visits for any negative gastrointestinal, behavioral, feeding, or other negative sequela suspected to result from our treatment. Participants will be asked to measure the child's weight using a digital home weight scale during tele-visits to monitor changes in weight.

Subjects will be considered “at risk” and reviewed by the medical monitor and site PI if either of the following two conditions. The medical monitor and site PI will determine if it is safe for the participant to continue in the study (or, under what conditions it may be safe for the participant to continue) given all patient characteristics, including baseline weight for height ratio or BMI percentile.

- 1) If more than 0.5 kg of weight is lost consistently per week over three consecutive weeks
- 2) If the subject experiences 10% loss of total body weight

If any negative outcomes are identified they will be reported to our Data Safety and Monitoring Board and proper steps will be taken.

CONFIDENTIAL

This material is strictly confidential and is intended solely for the guidance of clinical investigation. Do not disclose or use except as authorized in writing by the study sponsor

Children will also have laboratory measurements to assess megestrol safety.

- 1) Morning Cortisol. The blood for the morning cortisol test will be drawn before 8am by the local laboratory or mobile phlebotomy services to test for adrenal insufficiency. The test will take approximately 1 mL of blood and will be drawn at weeks 10 and 14 for all subjects. Participants taking inhaled or intranasal steroids will take an additional blood draw at week 0. If an abnormal value is measured, a repeat morning cortisol level will be obtained. Every effort should be made to complete a redraw at the earliest convenience, within 7 days. The medical monitor will be on the weekly team calls, so she will be able to advise based on specific circumstances. If the 2nd test is also abnormal, the study protocol will be paused, and a pediatric endocrinologist will be consulted to determine if a formal in-person consultation is needed with endocrinology. The subject may either resume the protocol or be removed from the study pending the endocrinologist and study team's assessment.

4 Subject Selection and Withdrawal

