To address Aim 1, analyses will be conducted using Generalized Linear Mixed Models with a logit link within SAS Proc GLIMMIX to model the binary outcome of transitioned to oral feeding (y/n) defined as at least 90 percent of calories consumed orally. Fixed effects (dummy variables) will be entered for each site as described by McNeish and Stapleton (2016) to account for the clustering of the participants within sites. This will result in essentially, a logistic regression model with appropriate standard errors. Sex, age at initiation, treatment condition, and interactions with treatment condition will enable us to examine the effect of group assignment on successful transition to oral feeding by week 24. Interactions between treatment group and sex will be examined but will not be sufficiently powered to reach definitive conclusions about sex differences. In addition to overall effects, subgroup analyses will be reported for males and females to examine treatment effects within sex groups.

To address Aim 2, we will determine whether any of our participants in either group have adrenal sufficiency levels outside of the normal range at any time point. Should any participant have levels outside of the normal range, we will descriptively examine the individual characteristics associated with this, including group assignment, medical diagnoses, sex, and age at initiation. These characteristics will be reported descriptively.

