8.1 Definitions

Unanticipated Problems Involving Risk to Subjects or Others

For the current study, we will use CTCAE criteria, incorporating the additional considerations about pediatric effects and regarding hospitalization. Any incident, experience, or outcome that meets all of the following criteria:

- Unexpected in nature, severity, or frequency (i.e. not described in study-related documents such as the IRB-approved protocol or consent form, the investigators brochure, etc.)
- Related or possibly related to participation in the research (i.e. possibly related means there is a reasonable possibility that the incident experience, or outcome may have been caused by the procedures involved in the research)

CONFIDENTIAL

This material is strictly confidential and is intended solely for the guidance of clinical investigation. Do not disclose or use except as authorized in writing by the study sponsor

- Suggests that the research places subjects or others at greater risk of harm (including physical, psychological, economic, or social harm).

Adverse Event

An **adverse event** (AE) is any symptom, sign, illness or experience that develops or worsens in severity during the course of the study. Intercurrent illnesses or injuries should be regarded as adverse events. Abnormal results of diagnostic procedures are considered to be adverse events if the abnormality:

- results in study withdrawal
- is associated with a serious adverse event
- is associated with clinical signs or symptoms
- leads to additional treatment or to further diagnostic tests
- is considered by the investigator to be of clinical significance

Serious Adverse Event

Adverse events are classified as serious or non-serious. A **serious adverse event** is any AE that is:

- fatal
- life-threatening
- requires or prolongs hospital stay
- results in persistent or significant disability or incapacity
- a congenital anomaly or birth defect
- an important medical event

Important medical events are those that may not be immediately life threatening, but are clearly of major clinical significance. They may jeopardize the subject, and may require intervention to prevent one of the other serious outcomes noted above. For example, drug overdose or abuse, a seizure that did not result in in-patient hospitalization, or intensive treatment of bronchospasm in an emergency department would typically be considered serious.

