All adverse events that do not meet any of the criteria for serious should be regarded as **non-serious adverse events**.

Adverse Event Reporting Period

The study period during which adverse events must be reported is normally defined as the period from the initiation of any study procedures to the end of the study treatment follow-up. For this study, the study treatment follow-up is defined as 30 days following the last administration of study treatment.

Preexisting Condition

A preexisting condition is one that is present at the start of the study. A preexisting condition should be recorded as an adverse event if the frequency, intensity, or the character of the condition worsens during the study period.

General Physical Examination Findings

At screening, any clinically significant abnormality should be recorded as a preexisting condition. At the end of the study, any new clinically significant findings/abnormalities that meet the definition of an adverse event must also be recorded and documented as an adverse event.

Post-study Adverse Event

All unresolved adverse events should be followed by the investigator until the events are resolved, the subject is lost to follow-up, or the adverse event is otherwise explained. At the last scheduled visit, the investigator should instruct each subject to report any subsequent event(s) that the subject, or the subject's personal physician, believes might reasonably be related to participation in this study. The investigator should notify the study sponsor of any death or adverse event occurring at any time after a subject has

CONFIDENTIAL

This material is strictly confidential and is intended solely for the guidance of clinical investigation. Do not disclose or use except as authorized in writing by the study sponsor

discontinued or terminated study participation that may reasonably be related to this study. The sponsor should also be notified if the investigator should become aware of the development of cancer or of a congenital anomaly in a subsequently conceived offspring of a subject that has participated in this study.

Abnormal Laboratory Values

A clinical laboratory abnormality should be documented as an adverse event if any one of the following conditions is met:

- The laboratory abnormality is not otherwise refuted by a repeat test to confirm the abnormality
- The abnormality suggests a disease and/or organ toxicity

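### The Aim 2 cortisol count mixes high and pre-dose values with the post-dose low values that could show megestrol suppression, and one stray value contradicts the all-in-range clause of Hypothesis 2A

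*Combined protocol and SAP*

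**What the plan says.** - **Hypothesis 2A (section 2, Study Aims).** Children randomized to megestrol "will not differ from control children in morning cortisol classification level (low, average, high) and will remain within the normal range at all time points". This has two parts: a between-arm comparison of three classes, and a range clause whose subject is the megestrol group.
- **Analyses 2B (section 2).** An exploratory look at which covariates "are related to abnormal morning cortisol levels". Abnormal is not defined.
- **Section 7.1, Planned Analyses, Aim 2.** The analysis asks "whether any of our participants in either group have adrenal sufficiency levels outside of the normal range at any time point". Any such child is then described by group assignment, diagnoses, sex and age. Direction, timing relative to dosing, the redraw and the three classes are not mentioned. The sample-size text in 7.1 declares all Aim 2 analyses descriptive.
- **Section 3.4.** The stated purpose of the test is adrenal insufficiency. All children are drawn at weeks 10 and 14; users of inhaled or intranasal steroids are also drawn at week 0. "If an abnormal value is measured, a repeat morning cortisol level will be obtained". "If the 2nd test is also abnormal, the study protocol will be paused".
- **Sections 6.4, 6.8 and 5.2.** The first dose waits until the week 10 cortisol is confirmed normal. The week 14 draw comes at least 5 days after the last dose. A child who stops early is drawn 5 days after the final dose.
- **Section 8.1.** A laboratory abnormality is an adverse event if any one of three conditions is met; the first is "The laboratory abnormality is not otherwise refuted by a repeat test to confirm the abnormality". The general adverse-event definition also covers an abnormal result that "leads to additional treatment or to further diagnostic tests".

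**The concern.** Aim 2 carries the trial's safety conclusion, and section 2 explains why: earlier work links a 6-week course to adrenal insufficiency in some children. The question is whether 4 weeks of megestrol leaves cortisol low. Only a low value after dosing bears on that.

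Followed as written, the count in 7.1 also includes two kinds of value that cannot bear on it: high values, and values from week 10 (or week 0) before any drug was given. Both occur by chance in both arms and dilute a real excess of low values on megestrol. The range clause in 2A is contradicted by a single stray value in either direction, including a pre-dose one. The part of 2A that would separate low from high, the class comparison, has no planned analysis.

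**Working it through.** The plan states no error rate, power or reference range for Aim 2, so there is no figure of its own to reproduce.

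**Inputs from the documents.** 30 children per arm (section 3.1); two scheduled draws per child, one pre-dose (week 10) and one post-dose (week 14). Week 0 draws are left out because the number of steroid users is not given.

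**Assumption.** A fraction p of draws from unaffected children falls outside the laboratory range, half of it low. A range holding 95% of unaffected children gives p = 5%; 2.5% and 1% are shown as well.

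**Step 1: the range clause of 2A, megestrol arm, no drug effect.** P(all in range) = (1 − p)^m, with m = 60 for both draws and m = 30 for week 14 alone.

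| p | m = 60 | m = 30 | expected out of range in 60 draws |
|---|---|---|---|
| 5% | .95^60 = 4.6% | .95^30 = 21% | 60 × .05 = 3.0 |
| 2.5% | .975^60 = 22% | .975^30 = 47% | 60 × .025 = 1.5 |
| 1% | .99^60 = 55% | .99^30 = 74% | 60 × .01 = 0.6 |

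The m = 60 column treats a child's two draws as independent. If they agreed completely, the result would equal the m = 30 column, so the two columns bracket the effect of positive correlation within a child.

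**Step 2: what the chance values are.** At p = 5%, the 3.0 expected in one arm split into 30 × .05 = 1.5 pre-dose, 30 × .025 = 0.75 post-dose high and 30 × .025 = 0.75 post-dose low. So 2.25 of 3.0, three quarters, cannot reflect suppression by the drug. The share is the same at any p if half of the out-of-range values are low.

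**Step 3: dilution.** Exact Fisher power (two-sided 5%, 30 per arm) serves here only as a yardstick, since no test is planned. Let megestrol cause a low week 14 value in a fraction d of children, with p = 5%.

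- Any abnormal value, any time: 1 − .95²(1 − d) against 1 − .95². For d = .20, 27.8% v 9.8%, power .31. For d = .30, 36.8% v 9.8%, power .62.
- Low at week 14, first value: 1 − .975(1 − d) against .025. For d = .20, 22.0% v 2.5%, power .46. For d = .30, 31.8% v 2.5%, power .82.

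**Step 4: should the count require confirmation?** Assume that 25% of chance low values repeat, so the control rate is .025 × .25 = .00625, and that a fraction r of suppressed children repeat low. The megestrol rate is 1 − (1 − .00625)(1 − dr). For d = .20, power is .54 if r = 1, .28 if r = .75 and .14 if r = .60. For d = .30 it is .89 if r = 1 and .43 if r = .60. The gain over Step 3 depends on nearly every suppressed child still being low at the redraw.

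**The case against.** The strongest reply is that Aim 2 is descriptive. With no alpha, margin or pass rule, nothing can formally fail, and the listing in 7.1 will show each flagged child's group. This stands, and it limits the harm to interpretation. It does not remove the point: 2A is stated as a hypothesis and will be judged against the data, and the characteristics listed in 7.1 do not include direction or timing relative to dosing.

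The chance figures also rest on an assumed reference range. At 1% per draw the range clause survives more often than not (55%). That stands too, which is why a range is given.

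A reader might infer several stronger points that the documents do not support:

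- *That the clause covers all 120 draws in both arms*, giving .95^120 = 0.2%. The subject of the sentence in 2A is the megestrol group, so 60 draws is the right count.
- *That the safety sections define abnormal as repeat-confirmed.* Section 3.4 calls the first value abnormal and uses the second to trigger a pause. In 8.1, not being refuted by a repeat is one of three alternative conditions. An operational trigger and a descriptive count may use different thresholds.
- *That the three classes conflict with the range.* They are compatible if average means in range. The gap is that the class comparison is hypothesised and not planned.
- *That only confirmed low values should count.* The redraw may come up to 7 days later, after a draw already at least 5 days off drug, so recovery in between is possible. Step 4 shows that confirmation can then lose more than it gains.

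**Conclusion.** The point holds as a defect in how the Aim 2 summary is defined. The count in 7.1 pools high with low and pre-dose with post-dose, although the test is for adrenal insufficiency and only the post-dose draw can show an effect of megestrol. Under the stated split, about three quarters of the chance abnormalities in an arm are irrelevant to the question. With no drug effect, the megestrol group meets the all-in-range clause with probability 4.6%, 22% or 55% at assumed out-of-range rates of 5%, 2.5% or 1% per draw (21%, 47% or 74% if only week 14 is counted).

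The plan also does not say whether the first or the repeat value enters Aim 2. An abnormal cortisol with a normal redraw has no clear adverse-event status: the redraw refutes it under one laboratory condition, yet the redraw itself might be read as a further diagnostic test.

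It would go too far to say that a safety test fails by chance, since no test is planned. The change is worth making because the conclusion on adrenal safety will be read from this count.

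**What to change.** Analysis wording only, in sections 2 and 7.1:

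1. Make the main Aim 2 summary the number and proportion of children in each arm with a low morning cortisol at the post-dose draw (week 14, or the post-stop draw in section 5.2), with the between-arm difference and an exact 95% confidence interval. State the lower limit, or whose laboratory limit applies. The interval keeps a clean result in proportion: even 0 of 30 low leaves a one-sided 95% upper limit of 1 − .05^(1/30) = 9.5%.
2. Report pre-dose values, high values and the redraw result (confirmed or not confirmed) separately by arm. Do not make confirmation a condition of the main count.
3. Drop the all-in-range clause from Hypothesis 2A.
4. Reconcile sections 3.4 and 8.1 on whether an abnormal cortisol with a normal redraw is an adverse event. The clinical actions in those sections need not change.

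No new data are needed, because every draw and redraw is already scheduled. The small cost is that high and pre-dose abnormal values leave the headline count, though they stay listed.

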6.4 Clinic Visit 2 (Week 10)

Participants will return to clinic to complete vital signs and blood draw (morning cortisol). If an abnormal morning cortisol value is measured, follow the redraw procedures under section 3.4 Primary Safety Endpoints. Height and weight will both be taken in triplicate via calibrated equipment by a trained staff member. Participants will bring in a frozen stool sample. Patients will be given megestrol or placebo, but asked to wait to administer the 1st dose until lab value for morning cortisol are confirmed normal. Megestrol will be dosed at 6 mg/kg/d at weeks 10-11, at 4 mg/kg/d at week 12, at 2 mg/kg/d at week 13, and fully tapered at the end of week 13. Participants will be asked to complete the PIP, ITQOL or CHQ, RAND SF-36, PedsQL and schedule three 24 hr Dietary recall phone calls over the coming week. Five

CONFIDENTIAL

This material is strictly confidential and is intended solely for the guidance of clinical investigation. Do not disclose or use except as authorized in writing by the study sponsor

days after the clinic visit, parents will begin to taper G or G/J tube feedings by 10% each day until they are stopped altogether. Families will be encouraged to contact team members with questions or concerns at any time throughout the study period.

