6.8 Clinic Visit 3 (Week 14)

Participants will return to clinic to complete vital signs and blood draw (morning cortisol). The morning cortisol lab value must be taken at least 5 days after the final dose of study drug, so verify with the family when the last dose will be taken before scheduling the Week 14 visit. If an abnormal morning cortisol value is measured, follow the redraw procedures under section 3.4 Primary Safety Endpoints. Height and weight will both be taken in triplicate via calibrated equipment by a trained staff member. At the visit they will also complete the PIP, ITQOL or CHQ, RAND SF-36, PedsQL and schedule three 24 hr Dietary recall phone calls over the coming week. Participants will bring in a frozen stool sample. Tube feedings and megestrol will have ceased. Parents will be asked about any major changes in their health, appetite, and medications

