7.1 Sample Size Determination and Statistical Methods

For Aim1 (To assess the efficacy of megestrol as part of the 24 week iKanEat protocol), if at least 90% of the treatment group successfully transitions (in pilot 100% successfully transitioned), with 72 participants, we would have .80 power to detect an odds ratio of .21. With 60 participants, we would have power to detect an odds ratio of .18. If only 75% of the treatment group successfully transitions, we will still have .80 power to detect an odds ratio of .25 with our smallest expected sample size of 60.

For Aim 2 (To assess the safety of megestrol as part of the 24 week iKanEat protocol), all analyses are descriptive, so a power analysis is not conducted.

For Aim 3 (To examine the effect of the transition from tube to oral feeding on parent stress and parent and child quality of life), with 60 participants, we would have .78 power to detect differences in slopes over the four data points equivalent to a standardized effect size of $d=.75$ or larger. With a sample size of 72, there will be .80 power to detect a difference in slopes equivalent to a standardized effect size of .70. To answer those questions in which the grouping factor is success in treatment, such as 3A (The transition to oral feeding will temporarily increase parent stress at week 14 at the cessation of tube feeding, with a return to baseline by week 24) and 3B (The transition to oral feeding will increase parent/child quality of life at 24 weeks compared to week 0), assuming that 60% of the participants across groups are successful, we would have sufficient power to detect effects equivalent to a standardized effect size of $d=.42$ or larger. With a sample size of 60, the minimum detectable effect size would increase to $d=.59$. If 70% percent are successful, with 72 participants we can detect effects equivalent to $d=.61$, and with 60 participants $d=.70$. These are moderate sized effects.

Planned Analyses

CONFIDENTIAL

This material is strictly confidential and is intended solely for the guidance of clinical investigation. Do not disclose or use except as authorized in writing by the study sponsor

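### The Aim 2 analysis does not estimate the between-arm cortisol comparison in Hypothesis 2A and does not separate pre-drug from post-drug values

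*Combined protocol and SAP*

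**What the plan says.** Section 2 (Study Aims) states Hypothesis 2A in two parts. Children on megestrol "will not differ from control children in morning cortisol classification level", the classes being low, average and high, and they "will remain within the normal range at all time points". Exploratory analysis 2B looks for covariates of abnormal morning cortisol.

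Section 7.1 says of Aim 2 that "all analyses are descriptive, so a power analysis is not conducted". The planned analysis determines whether any participants in either group "have adrenal sufficiency levels outside of the normal range at any time point". If there are any, "we will descriptively examine the individual characteristics associated with this, including group assignment, medical diagnoses, sex, and age at initiation".

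The timing of the draws is set elsewhere:

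- Section 3.4: all children are drawn at weeks 10 and 14, users of inhaled or intranasal steroids also at week 0, and an abnormal value is repeated.
- Section 6.4: at week 10 families receive the study drug but are "asked to wait to administer the 1st dose until lab value for morning cortisol are confirmed normal".
- Section 6.8: "The morning cortisol lab value must be taken at least 5 days after the final dose of study drug" at the week 14 visit.
- Section 5.2: whenever the drug is stopped, a cortisol is taken 5 days after the final dose.

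**The concern.** The first part of 2A is a statement about two arms and three classes. The analysis assigned to it is a list of out-of-range children in which arm is one descriptor beside diagnosis, sex and age. Nothing in Section 7.1 produces the quantity that 2A is about.

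The list also runs over every draw. The week 0 and week 10 draws precede the first dose. A child assigned to megestrol with an abnormal week 10 value and a normal repeat would contradict 2A before taking any drug, and would count as a case in 2B.

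Safety of the 4-week course is the second aim. Section 2 motivates it by adrenal insufficiency seen in some children on a 6-week course, and ties the efficacy and safety results to wider dissemination. A result on this point should be attributable to the drug and should carry its uncertainty.

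**Working it through.** The documents give no rate, margin, power or interval for Aim 2, so there is no figure to reproduce. The check sets the hypothesis against the analysis, places each draw relative to the drug, and then asks how much 30 per arm can show.

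**1. Hypothesis against analysis**

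| Hypothesis 2A needs | Section 7.1 provides |
|---|---|
| A comparison between arms | Arm as one descriptor among out-of-range children |
| Low / average / high | In or out of range only |
| Evidence on the size of any difference | No proportion by arm, difference, interval or margin |
| Values normal at every time point | Addressed by the any-time-point listing |

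Only the last row is matched.

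**2. Draws against drug exposure**

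| Draw | Who | Relative to study drug |
|---|---|---|
| Week 0 | Inhaled or intranasal steroid users | Before |
| Week 10 | All | Before; first dose waits for a normal result |
| Week 14 | All | At least 5 days after the last dose |
| 5 days after final dose | Early stoppers (Section 5.2) | After |
| Repeat | Any child with an abnormal value (Section 3.4) | Same side as the draw it repeats |

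Section 7.1 does not distinguish the rows.

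**3. What zero cases would show.** Input: n = 30 per arm (Section 3.1).

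- Exact two-sided 95% upper limit for 0/n: 1 - 0.025^(1/n). For n = 30 this is 11.6%.
- Chance of seeing no case if the true rate were 5% (an assumed rate): 0.95^30 = 0.215.
- Newcombe score interval for 0/n against 0/n: the half-width is the Wilson upper limit, z²/(n + z²). With z² = 3.84 and n = 30, this is 3.84/33.84 = 0.114, so -11.4 to +11.4 points.

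Range over plausible numbers: 36 per arm is half of the 72 to be recruited (Section 4.3), and 24 per arm is 30 less 20%.

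| n per arm | Upper limit for 0/n | Interval for 0/n vs 0/n |
|---|---|---|
| 24 | 14.2% | ±13.8 points |
| 30 | 11.6% | ±11.4 points |
| 36 | 9.7% | ±9.6 points |

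**4. What a few cases would show.** Suppose 5/30 on megestrol and 1/30 on placebo. The difference is 16.7% - 3.3% = +13.3 points, with a Newcombe 95% interval of -2.9 to +30.5. A list of six children would convey neither figure.

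**5. What a no-difference claim would need.** Assume a 5% rate in both arms, a 10-point margin, one-sided 0.025 and 80% power. Then n = (1.96 + 0.84)² × 2 × 0.05 × 0.95 / 0.10², or about 75 per arm. At the same assumed rate, 15 points needs 34 and 20 points needs 19.

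**6. Effect of including pre-drug values, if an any-visit rate were formed.** The plan does not define such a rate, so this is an illustration only. Assume post-drug rates of 20% and 5%, and a 10% chance of a pre-drug abnormality in both arms, independent of the post-drug result. The any-visit rates are 1 - 0.90 × 0.80 = 28% and 1 - 0.90 × 0.95 = 14.5%. The ratio falls from 4.0 to 1.9 and the difference from 15 to 13.5 points. For pre-drug rates of 5% to 20% the ratio is 2.5 to 1.5. The size depends on these assumed rates; the direction does not.

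**The case against.** The strongest defence is that the plan is open about what it does. It calls Aim 2 descriptive and forgoes a power analysis, which is acceptable for a safety aim with 60 children. The any-time-point wording follows the second part of 2A, so it is not in itself a slip. Each draw belongs to a visit, so an analyst could recognise a week 0 or week 10 value as pre-drug. Pre-drug abnormalities should be similar in the two arms by randomisation. Analysis 2B is labelled exploratory. Reporting an interval also does not make 30 per arm more informative.

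All of that stands, and it limits the point. It does not supply the missing between-arm summary or the missing separation of draws. That an analyst could make the split later is not a specification.

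Three stronger readings are tempting and are not supported:

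- A reader might infer that the plan will declare megestrol safe if few or no cases appear. No section says so; 2A is a hypothesis, not a conclusion.
- A reader might infer that the plan pools pre-drug and post-drug values into a rate for each arm, or that this biases the comparison. No pooled rate is defined. The fault is that the draws are not separated, and the likely effect is noise and dilution.
- A reader might infer that week 14 is the only post-drug value. It is the only routinely scheduled one, but Section 5.2 adds the early-stop draw and Section 3.4 the repeat.

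**Conclusion.** The point holds as a mismatch between hypothesis and analysis. The first part of 2A concerns arms and classes, and the Aim 2 analysis estimates neither. The second part is addressed, but in a way that lets values taken before any drug count against it and enter 2B.

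The size of the uncertainty is set by the sample: about ±11 points for the difference, and an upper limit of 11.6%, if no abnormal value is seen with 30 per arm. These two figures need only the planned sample size and a conventional 95% level. The 5% rate, the margins and the pre-drug rates used above are assumptions, because the documents give none, and the conclusion does not rest on them. The collected data remain usable, so this should be corrected in the plan but does not threaten the trial.

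**What to change.** In the Aim 2 paragraph of Section 7.1:

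- Analyse children who received at least one dose, which is the all-treated population the plan already defines.
- Report, by arm, the proportion low, average and high at the post-drug draw. That is week 14, or for early stoppers the draw 5 days after the final dose under Section 5.2.
- Give the arm difference in the proportion with abnormal cortisol, with a score or exact 95% interval.
- Report the initial post-drug value and, separately, abnormality confirmed on the Section 3.4 repeat. Section 8.1 already takes account of a repeat test when deciding whether a laboratory abnormality is recorded as an adverse event.
- List weeks 0 and 10 as pre-drug baseline, and run 2B on post-drug abnormality only.

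In Section 2, reword 2A as estimating the arm difference in post-drug abnormal cortisol, and remove the prediction of no difference.

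The cost is a change of wording. No draw, child or clinical procedure is added, and no test or power claim is needed. The drawback is that the safety statement will look less certain: the change shows the imprecision of 30 per arm but does not reduce it.
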